3.5 Project timeline

- October 2022-October 2023: Develop and pilot the intervention.
- November 2023- November 2024: Collect data and run the intervention.
- 2025-2027: Analyse and publish results.

3.6 Participant timeline

The time schedule of enrolment, interventions and assessments for participants is shown in Figure 2.

Figure 2. Schedule of enrolment, intervention, and assessments.

TIMEPOINT	Enrolment	Allocation	Post-allocation				
	Nov. 2023	Nov. 2023	Nov. 2023	Jan. 2024	Feb. 2024	Mar. 2024	Nov. 2024
ENROLMENT:							
Informed consent	X						
Allocation		X					
INTERVENTION – FIRST GROUP				→			
INTERVENTION – SECOND GROUP:					→		
ASSESSMENTS:							
Questionnaires on health & wellbeing			X	X	X	X	X
Socio-demographics			x			X	
Feasibility & fidelity				X (1st group)	X (2nd group)		

3.7 Sample size

During the study period, there will be approximately 3,300 pupils in grade 5 to 10 in the public schools in Moss, who will be invited to participate. We have a conservative estimate of 70 % participation, i.e., about 2,300 participants. All pupils in 157 school classes in Moss municipality will be invited to participate in our study. The average number of pupils in a school class in Moss is 21, and we assume that 15 pupils per class (i.e., 70 %) participate.

Estimating statistical power in a clustered trial that is not randomized can be challenging, as we need to account for the correlation within clusters and the variation between clusters, as well as the variation in the outcome measure(s). Our approach to determine statistical power was to run a power analysis available at <http://psychstat.org/crt2arm> with the following assumptions:

- Sample size (i.e., number of participating pupils per class): 15
- Effect size: 0.16
- Number of clusters (i.e., number of school classes); 157
- Intra-class correlation: 0.05

- Significance level: 0.05
- Power curve: No power curve
- H1: Two-sided test

This analysis resulted in a power of 0.8411. The assumption that our intervention might have an effect size of 0.16 is based on previous studies, see (Tanner-Smith et al., 2018; Taylor et al., 2017; Werner-Seidler et al., 2017).

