The purpose of the current study is to develop an evidence-based, health-promoting intervention and investigate its effects on well-being and mental health among school pupils aged 10 to 16 in Moss municipality, Norway.

In the first phase of the study, we will pilot the intervention at two selected schools in Råde municipality. In the second phase of the study, we will run a full-scale trial at the public schools in Moss (16 schools; approximately 3,300 pupils). For the latter purpose, we will use the quasi-experimental Extended Selection Cohorts design. We will investigate the changes in the pupils' scores on health behaviours, mental health, and well-being from baseline to different timepoints of data collection during a 12 months follow-up period.

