2.3 Trial design

In phase 1, we will conduct a pilot study in two chosen schools in Råde Municipality.

In phase 2, we will use the quasi-experimental Extended Selection Cohorts (ESC) design. The ESC design is an option for real-life settings when an RCT is not feasible, because the ESC design makes it possible to compare same-age treatment groups. For the current study, a cluster-RCT of sufficient power would have needed a large number of schools and is therefore not feasible. The ESC design is a cohort-longitudinal design with adjacent cohorts, that are measured at two or more time points; a design that has been used to evaluate effects of school-based interventions, for example anti-bullying programmes (Kärnä et al., 2011; Olweus, 2005) and a programme that promotes physical activity and a healthy diet (Takens et al., 2020). Each cohort comprises subjects of approximately the same age. In a standard RCT design, the pupils, classes, or schools are randomly allocated to different intervention and control groups; but in the ESC design intervention and control groups belong to the same schools, and fewer schools or pupils are therefore needed. The cohorts that are exposed to the intervention are compared with unexposed cohorts from the same school, ensuring that the research subjects are recruited from a relatively stable population with the same socio-demographic characteristics (Olweus, 2005; Takens et al., 2020). This is important when studying health and health behaviour, which differs according to different SES and ethnicity groups. The ESC design does not, however, allow us to control for general societal time trends that coincide with the intervention.

In our study, we will collect data from each cohort (i.e., school grade) five times, starting in November, 2023 (baseline), followed by January, February, March, and November, 2024.

At 12 months follow-up, each cohort will be compared to the same-age adjacent baseline cohort group (see Figure 1). For instance, the measures of the grade 5 cohorts that will have been *exposed* to the intervention (grade 5 in 2024–2025) will be compared to the baseline measures of the *unexposed* grade 5 cohorts (grade 5 in 2023–2024).

Figure 1. How exposed cohorts can be compared to unexposed cohorts at 12 months follow-up

	Cohort A	Cohort B	Cohort C	Cohort D	Cohort E	Cohort F
Baseline (Nov. 2023)	Grade 5	Grade 6	Grade 7	Grade 8	Grade 9	Grade 10
Intervention						

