Follow-up (Nov. 2024)	Grade 6	Grade 7	Grade 8	Grade 9	Grade 10	

In order to separate any effects of the intervention from changes in variables due to other causes, we will apply a «wait list control group» element, i.e., delayed intervention: approximately $\frac{1}{2}$ of the schools will start the intervention in November 2023, while the remaining schools will start the intervention approx. 14 weeks later. We will collect data from all pupils in November 2023, and in February 2024 we will compare the scores of the intervention group with the «wait list» group.

3 Methods

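### The single power figure of 0.8411 is tied to no outcome or comparison, leaves out the school level, and does not describe the February wait-list contrast or the 12-month cohort contrast

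*Combined protocol and SAP*

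**What the plan says.** Section 3.7 lists the inputs to an online two-arm cluster calculator: 15 pupils per class, effect size 0.16, ICC 0.05, two-sided 5% level, and "Number of clusters (i.e., number of school classes); 157". It concludes: "This analysis resulted in a power of 0.8411". It names no outcome, time point or pair of groups.

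The plan has two effect contrasts, both in section 2.3.

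- **February 2024 wait list.** About half of the schools start in November 2023 and "the remaining schools will start the intervention approx. 14 weeks later". Then "in February 2024 we will compare the scores of the intervention group" with those of the waiting schools. Section 2.1 describes a "full-scale trial at the public schools in Moss (16 schools; approximately 3,300 pupils", so this is about 8 schools against 8.
- **12 months.** Here "each cohort will be compared to the same-age adjacent baseline cohort group". Figure 1 gives five such pairs, grades 6 to 10. The two sides are not separate samples, because "in the ESC design intervention and control groups belong to the same schools", and cohorts B to E supply an exposed follow-up to one pair and an unexposed baseline to another.

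Section 3.11 plans a multilevel model with class as level 3 and school as level 4, and subgroup analyses by grade.

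**The concern.** A power figure belongs to a particular contrast. Here the calculation uses classes as the allocated units and has no school variance. Yet the wait list is assigned by school, and the analysis model recognises a school level. The 12-month contrast is not a division of 157 classes into two arms at all. One grade has far fewer classes, and the pooled version measures most cohorts twice.

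Recruitment does not depend on the figure, because every eligible pupil is invited. What depends on it is how a null result is read, since section 3.7 is the plan's only statement of what the study can detect. February matters particularly. Section 2.3 concedes that the cohort design does not "allow us to control for general societal time trends that coincide with the intervention", and adds the wait list to separate intervention effects from other causes of change.

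**Working it through.** **Inputs from the plan:** d = 0.16, 15 pupils per class, total ICC 0.05, 157 classes, two-sided 5% (section 3.7); 16 schools (section 2.1); six grades and five pairs (Figure 1). **Assumptions, because the documents give no values:** school ICCs, correlations over time, equal school sizes, an even spread of classes over grades. Power is from the noncentral t distribution.

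**1. The plan's figure.** Variance of a class mean: 0.05 + 0.95/15 = 0.1133. SE = sqrt(4 × 0.1133/157) = 0.0537; noncentrality 0.16/0.0537 = 2.98; 155 df. Power = 0.8411, as stated.

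**2. February, 16 schools.** Per school: 157/16 = 9.81 classes and 147.2 pupils. With school ICC s, class ICC 0.05 − s, and baseline correlations rc (school and class) and rp (pupil):

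Var = s(1 − rc²) + (0.05 − s)(1 − rc²)/9.81 + 0.95(1 − rp²)/147.2; SE = sqrt(4 × Var/16); 14 df.

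| School ICC s | 0 | 0.005 | 0.01 | 0.02 | 0.03 |
|---|---|---|---|---|---|
| Unadjusted | 0.79 | 0.65 | 0.55 | 0.41 | 0.33 |
| Adjusted, rp 0.6, rc 0.5 | 0.92 | 0.80 | 0.69 | 0.53 | 0.43 |
| Adjusted, rp 0.6, rc 0.7 | 0.95 | 0.88 | 0.80 | 0.66 | 0.55 |
| Adjusted, rp 0.6, rc 0.9 | 0.99 | 0.97 | 0.95 | 0.90 | 0.84 |

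The unadjusted value at s = 0 has the same SE as the plan's calculation (0.0537). The fall from 0.84 to 0.79 comes only from using 14 df instead of 155.

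**3. 12 months, one grade.** 157/6 = 26.17 classes and 392.5 pupils per side. Variance per side v = 0.1133/26.17 = 0.00433; SE = sqrt(2v) = 0.0931; noncentrality 1.72; 50 df. Power = 0.39. The effect detectable with 80% power is 0.27.

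With shared schools, where S schools teach the grade and rs is the correlation of school effects between the two sides: Var = 2[(0.05 − s)/26.17 + 0.95/392.5] + 2s(1 − rs)/S. Taking s from 0 to 0.03, rs from 0 to 1, and df of S − 1 or 50:

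- S = 16 (every school teaches every grade): 0.32 to 0.50
- S = 8: 0.22 to 0.50
- S = 5: 0.15 to 0.50

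**4. 12 months, five pairs pooled.** With independent sides, Var = 10v/25; SE = 0.0416; noncentrality 3.84; 260 df. Power = 0.97.

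Allowing for cohorts B to E on both sides, with correlation r between a cohort's two means, Var = [2v + 8v(1 − r)]/25. At r = 0.5, SE = 0.0322 and power is above 0.99, whether 155 or 15 df are used.

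If schools also differ in change, add 2s(1 − rs)/16, set the class ICC to 0.05 − s, and use 15 df:

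- r 0.5, s 0.01, rs 0.7: 0.98
- r 0.5, s 0.03, rs 0.5: 0.83
- r 0, s 0.03, rs 0.5: 0.76

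**5. Loss of pupils.** The plan's calculation has no dropout. At an assumed 12 pupils per class on both sides, 0.39 becomes 0.35 and the independent-sides 0.97 becomes 0.95.

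**The case against.** The strongest reply is that the calculation is correct and roughly fits the wait list: 157 classes in two groups is what the calculator assumes, and the stated inputs alone do give 0.84 for February at class level. That stands. Every other February value needs school-level df, a school ICC or baseline correlations that the plan does not state. The narrower criticism remains: the split is by school, and the calculation omits that level.

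A second reply is that the plan never attaches 0.84 to a single grade, and that grade appears in section 3.11 only as a subgroup. That is true, and a reader should not infer that the plan promises 84% power per grade. But section 2.3 describes the 12-month comparison cohort by cohort, and no other figure is offered for it.

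Third, the ranges depend on choices. The 0.32 to 0.50 for one grade is not a general bound, because it assumes that all 16 schools teach every grade, and the 0.97 ignores the overlap of cohorts. Both limits are fair and are shown in the working.

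Finally, recruitment is a census, section 3.7 admits that power is hard to estimate here, and a null result should be read mainly from its confidence interval. This limits the consequence but does not make the figure apply to either contrast.

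**Conclusion.** The point holds as a fault in the power justification, and it should be fixed. The figure of 0.8411 is right for a design that neither contrast has.

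- **One grade at 12 months:** 0.84 is far too high. Power is about 0.39 and no more than about 0.50 in any school-sharing scenario tried. It is lower if fewer schools teach each grade or pupils are lost. This rests on an even spread of classes over grades.
- **Pooled 12 months:** 0.84 is too low if the sides are independent (0.97) or the repeated cohorts correlate (above 0.99). It is about right or too high if schools differ substantially in change (0.83 to 0.76).
- **February:** the direction is not determined by the documents. Power is below 0.84 at modest school ICCs unless baseline adjustment is strong, and above it when school variance is near zero or clusters are very stable.

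Three stronger readings are tempting and are not supported. There is no arithmetic slip, because the figure reproduces to four decimals. The documents do not show that the trial as a whole, or February in particular, is underpowered. Nor do the plan's own inputs produce the February spread, which comes from the labelled assumptions.

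**What to change.** In section 3.7, replace 0.8411 with separate figures or ranges, each tied to a named outcome:

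- **February contrast:** school as the allocated unit (16 schools), a labelled range of school ICCs, unadjusted and baseline-adjusted.
- **12-month contrast:** one figure for a single same-grade pair and one pooled over the Figure 1 pairs, allowing for shared schools and for cohorts B to E on both sides. Say which of the two is the main 12-month comparison.
- **Assumptions:** list classes per grade, schools per grade, correlations over time and dropout.

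In section 3.11, say that inference for February rests on the number of schools. More than one model can do this, and the point does not require a particular one. Section 4.5 leaves school name and class membership out of the final dataset, so state that coded school and class identifiers are kept for analysis.

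The cost is recalculation, wording and the coded identifiers, with no extra pupils or schools. The downside is that several figures, some possibly less favourable, replace one.

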3.8 Recruitment

The teaching programme will take place at school, during ordinary teaching hours. The Head of education in Moss municipality has decided to use the teaching programme in the interdisciplinary topic of public health and life skills for all pupils in 5th to 10th grade. All pupils in these grades will consequently be exposed to the teaching programme. All pupils in 5th to 10th grade in the public schools in Moss will be invited to complete questionnaires, except pupils attending a special education school (N=18).

Teachers who deliver the intervention will be invited to complete questionnaires.

Some teachers, school nurses, school leaders, and parents will be invited to participate in focus group interviews.

3.9 Data collection methods

We will collect quantitative data by asking the pupils to complete web-based questionnaires at school, in the same way that many of them are used to complete as part of the Ungdata survey. We will use “Nettskjema” to collect data. “Nettskjema” is a digital survey system developed by the University Center for Information Technology (USIT) at the University of Oslo. Responses from the questionnaire will be sent directly and encrypted (asymmetric encryption) to USIT’s Services for Sensitive Data (TSD). TSD is developed to store and analyse sensitive research data in accordance with Norwegian and European data protection laws and the Health Research Act.

“Nettskjema” will also be used to collect questionnaire data from teachers who deliver the intervention. Here, no personal identifying information will be collected from the teachers.

Researchers will take written notes during the focus group interviews. Here, no personal identifying information will be collected or included in written notes.

3.10 Data management

Data will be stored and analysed in TSD, which is a platform for collecting, storing, analysing and sharing sensitive data in compliance with the Norwegian privacy regulation. TSD offers virtual servers and backup- and storage systems with very high safety standards.

Students and teachers will be invited sign in through their digital Feide school account. Feide is the national solution for secure login and data sharing in education and research in Norway.

With Feide, pupils, students, researchers and teachers get safe and correct access to a number of different digital services with one username and password. TSD will ensure that every Feide username will be automatically encrypted with an encryption key unique to this project, and the encrypted username will act as the student’s or teacher’s serial number in the data file. The data file is located on a secure server at TSD and will not contain identifiers such as names, Feide usernames or national ID numbers. The project manager and staff (named in point 1.7) will be given access to the data file to analyse data on TSD’s server. The researchers will not be able to identify individual students or teachers on the basis of the data file.

3.11 Statistical Analysis Plan

To analyse the effect of the intervention we will use multilevel regression. In these analyses individual measurements at the five timepoints are nested within pupils (level 2), which in turn are nested within classes (level 3), in turn nested within schools (level 4). We will use linear multilevel regression for all continuous outcome measures, and logistic multilevel regression for categorical outcome variables.

Multilevel models are ideally suited for clustered and longitudinal data, where the common assumption of independence of measures does not hold. The models also perform well with missing data, and can be used to investigate both general trends, and factors underlying the variability observed at various levels in the hierarchy.

Based on previous research we hypothesize that the effects of the intervention will be greater for individuals who score lower on wellbeing measures and/or higher on mental health symptoms at baseline. We will therefore stratify our sample based on the participants' wellbeing scores and their mental health symptoms score and perform subgroup analysis. We also hypothesize that the effects of the intervention will be greater for younger participants, and we will therefore perform subgroup analysis based on school grade (as a proxy for participants' age).

To explore the moderation effects by SES, gender, age in years, ethnicity, baseline level of mental health symptoms, loneliness, wellbeing level, and leisure activities level, we will add interaction terms to the model. When these terms are significant, we will stratify the analyses for specific subgroups.

A significance level of $p = 0.05$ will be used. For the analyses we will use Stata v. 18, IBM SPSS Statistics v. 25.0, and R 3.5.3.

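### Section 3.11 names no class-by-wave or school-by-wave variance, so a literal fit makes the standard error of the 12-month same-grade contrast too small

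*Combined protocol and SAP*

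**What the plan says.** Section 3.11 plans multilevel regression, linear for continuous outcomes and logistic for categorical ones. The hierarchy is "individual measurements at the five timepoints are nested within pupils (level 2), which in turn are nested within classes (level 3"), and the classes are "in turn nested within schools (level 4"). There is no model equation and no list of random effects. No random slope, class-by-wave or school-by-wave term, robust variance or small-sample correction is named. The threshold is plain: "A significance level of $p = 0.05$ will be used".

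Section 2.3 defines the long-term test: "At 12 months follow-up, each cohort will be compared to the same-age adjacent baseline cohort group". A grade surveyed after exposure in November 2024 is set against the same grade surveyed before exposure in November 2023, in the same schools. On change over time, section 2.3 concedes only that society-wide trends are uncontrolled. Change specific to a class or school is not mentioned.

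Section 3.7 gives a single intra-class correlation of 0.05, with no split between class and school and no correlation across waves.

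**The concern.** Naming levels tells the analyst where variance may sit, not which effects may vary over time. The most literal fit is a random intercept for pupil, class and school. That fit gives each class and school the same departure at all five waves, and treats classmates' changes between waves as independent.

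Most pupils contribute to both November surveys, so a model-based estimate of the 12-month contrast draws heavily on within-pupil change, where constant class and school intercepts largely drop out. If a class or school moves as a unit over the year, that movement has nowhere to go but the pupil residual. There it is averaged over roughly 2,000 pupils rather than about 130 classes or 16 schools. Such movement is plausible over 12 months: the lessons are given by each class's own teacher (section 3.3), and one cohort passes from grade 7 to grade 8 (Figure 1).

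At stake is the long-term part of objective 8. Its confidence intervals would be too narrow and its false-positive rate above the stated 0.05.

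**Working it through.** **Inputs from the documents.** Section 3.7: "Sample size (i.e., number of participating pupils per class): 15"; "Number of clusters (i.e., number of school classes); 157"; "Significance level: 0.05"; "H1: Two-sided test"; effect size 0.16; intra-class correlation (ICC) 0.05; stated power 0.8411. Section 2.1: 16 schools. Section 2.3: five waves, with the 12-month contrast between same-grade cohorts.

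**Assumed, because the documents do not give them.** Class autocorrelation across waves (CAC) 0.5 to 0.9; pupil autocorrelation (rho) 0.5 to 0.7; total variance 1; 12 primary and 4 lower-secondary schools; about 26 classes per grade; equal class sizes, no dropout and unchanged class labels.

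**Step 1: the plan's own figure.** Noncentrality = d × sqrt(J / (4 × (ICC + (1 − ICC)/m))) = 0.16 × sqrt(157 / (4 × (0.05 + 0.95/15))) = 2.978. A two-sided noncentral t with 155 degrees of freedom gives power 0.8411, as stated. This is a single-timepoint calculation and says nothing about stability across waves.

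**Step 2: simple before-after change, class-level change only.** Let c = ICC × (1 − CAC) be the class-by-wave variance and e = (1 − ICC) × (1 − rho) the residual. The ratio of true to model variance is (e + m·c)/(e + c), and the true error rate is 2 × (1 − Φ(1.96/√ratio)).

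| CAC, rho | c | e | ratio | error rate |
|---|---|---|---|---|
| 0.9, 0.5 | 0.005 | 0.475 | 1.146 | 6.7% |
| 0.8, 0.6 | 0.010 | 0.380 | 1.359 | 9.3% |
| 0.5, 0.7 | 0.025 | 0.285 | 2.129 | 17.9% |

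**Step 3: the plan's same-grade contrast.** Generalised least squares over five waves, with wave and grade-at-survey as fixed effects. The random-intercept model variance is compared with the sandwich variance when class-by-wave change (and then school-by-wave change) is present. The same error-rate formula applies. The rates were checked in five scenarios by finding numerically the variance values that the misspecified model would settle on; they agreed to within 0.1 percentage point.

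| CAC, rho | class ICC 0.05: model SE / true SE, error | class 0.04 + school 0.01: model SE / true SE, error |
|---|---|---|
| 0.9, 0.5 | 0.0253 / 0.0266, 6.2% | 0.0275 / 0.0311, 8.3% |
| 0.8, 0.6 | 0.0236 / 0.0263, 7.8% | 0.0259 / 0.0330, 12.4% |
| 0.5, 0.7 | 0.0216 / 0.0283, 13.5% | 0.0235 / 0.0400, 25.0% |

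With CAC = 1 the rate is 5.0% in every row. Class-only rates are lower than in step 2 because part of the variance of this contrast is between-class difference that the model already includes.

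**Step 4: a second parametrisation, November surveys only.** School variance 0.01, class 0.04, pupil 0.55, residual 0.40.

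| class-by-wave | school-by-wave | model SE | true SE | error rate |
|---|---|---|---|---|
| 0 | 0 | 0.027 | 0.027 | 5.0% |
| 0.01 | 0 | 0.027 | 0.030 | 7.3% |
| 0.01 | 0.0025 | 0.027 | 0.037 | 14% |
| 0.01 | 0.005 | 0.027 | 0.042 | 20% |
| 0 | 0.0025 | 0.027 | 0.034 | 12% |
| 0 | 0.005 | 0.027 | 0.040 | 18% |

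The last two rows show that school-level change drives the larger values.

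**Step 5: power once the standard error is honest.** In the worst case of step 4, 0.16/0.0421 = 3.80, and Φ(3.80 − 1.96) = 0.967. With a t reference on 15 degrees of freedom (16 schools less one) the power is 0.944.

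**The case against.** The strongest reply is that section 3.11 never says that only intercepts vary. Class- and school-level time effects are ordinary multilevel regression and fit its wording, and the section mentions studying variability at the various levels of the hierarchy. This stands. A reader might infer that the plan prescribes a class effect held constant over all five waves, but the text does not support that. The random-effects structure is unspecified, and the plan permits the faulty fit without requiring it.

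Second, the error rates rest on quantities absent from the documents. This also stands. A reader might infer a definite true error rate, such as 7 to 19%, but no such band is a property of the plan. With perfectly stable classes and schools the rate is 5%.

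Third, change shared by classmates alone does modest damage (7.3% in step 4). The larger values need school-wide shifts, for whose size the documents give no evidence. That is right, and the two sources should be reported separately.

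Fourth, the same-grade comparison is partly between different pupils, so class intercepts do not cancel entirely. That is true, and step 3 allows for it. The rates fall but stay above 5% whenever class or school effects are not perfectly stable.

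Finally, the contrast already carries the admitted threat from societal trends. That is a question of bias. It does not excuse a standard error that leaves out a plausible component.

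**Conclusion.** The point holds as an omission with a conditional consequence. Section 3.11 names nesting levels only. Fitted literally with random intercepts, it understates the standard error of the 12-month same-grade contrast whenever classes or schools change as units between waves.

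Over CAC 0.5 to 0.9 and rho 0.5 to 0.7, the true error rate of the nominal 5% test is about 6 to 13% with class-level change only, and about 8 to 25% with school-level change added at a school ICC of 0.01. It is 5% if both are perfectly stable. These figures also rest on the assumed school split, equal classes, no dropout and stable class labels. The direction is secure; the size is unknown until across-wave correlations are available.

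This should be fixed, because the choice of random effects could otherwise be made after seeing the data. It concerns precision, not bias, and does not undermine the design.

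**What to change.** In section 3.11:

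- State that class-by-wave and school-by-wave random effects are included, alongside the pupil, class and school intercepts, in the models for both the 12-month same-grade contrast and the start-group contrast, linear and logistic alike.
- Name the fallback if the model does not converge: school-clustered robust standard errors with a small-sample correction for 16 schools. With so few schools an uncorrected robust variance would not be adequate.
- Define class and school membership at each wave. Cohort C moves from grade 7 to grade 8 between the two November surveys, and if those pupils change class or school, strict nesting over five waves fails.
- Keep coded class and school identifiers in the analysis file, and reconcile this with section 4.5, which excludes school name and class membership from the final dataset. Without coded identifiers, even the levels already planned cannot be fitted.

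The cost is SAP wording, two more variance components and somewhat wider intervals: in the step 4 scenarios that include class-level change, the standard error goes from about 0.027 to between 0.030 and 0.042. Pooled 12-month power for 0.16 remains about 0.97 on a normal reference in the worst of these, and about 0.94 on 15 degrees of freedom. No extra data collection is needed.

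### The 12-month contrast compares year groups within a school, but the 3.11 model has no year-group level, so intervals may be too narrow, mainly for single grades

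*Combined protocol and SAP*

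**What the plan says.** Section 2.3 (Trial design) defines the contrast: "At 12 months follow-up, each cohort will be compared to the same-age adjacent baseline cohort group". It places both sides in the same schools: "The cohorts that are exposed to the intervention are compared with unexposed cohorts from the same school". A cohort is a school grade, and Figure 1 gives five such contrasts, for grades 6 to 10 in November 2024.

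Section 3.11 (Statistical Analysis Plan) lists the levels of the model. Measurements are "nested within pupils (level 2), which in turn are nested within classes (level 3), in turn nested within schools (level 4". No year-group term, cluster-robust variance or small-sample correction is mentioned, and the fixed part that would express the 12-month contrast is not written out. On the hypothesis that younger pupils benefit more, the same section plans to "perform subgroup analysis based on school grade (as a proxy for participants' age".

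Section 3.7 (Sample size) uses a single ICC of 0.05 with "Number of clusters (i.e., number of school classes); 157" and "Sample size (i.e., number of participating pupils per class): 15". Section 2.1 speaks of "public schools in Moss (16 schools; approximately 3,300 pupils". Section 4.5 (Confidentiality) says that the final dataset will not contain school name or class membership.

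**The concern.** In the 12-month contrast, exposure varies between year groups within a school, and that is a level the model does not have. Parallel classes of a year group share intake, teaching team and events. Both sides of the contrast come from the same school, so the school intercept drops out and cannot represent what those classes share. The model then treats them as independent.

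An unusually strong or weak year group could be read as a programme effect with an interval that is too short. Objective 8 (immediate and long-term effects) is exposed to this. The grade-specific analyses are exposed most, because each 12-month grade contrast rests on one pair of year groups per school.

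**Working it through.** **1. The plan's own figure.** For a two-arm cluster trial, λ = √[J·d² / (4·ICC + 4(1−ICC)/n)]. With J = 157, d = 0.16, ICC = 0.05 and n = 15, this is √(4.0192/0.4533) = 2.978. On 155 degrees of freedom the power is 0.8411, as stated in 3.7. The calculation takes all 157 classes as independent.

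**2. Parallel classes must exist.** 16 schools × 6 grades gives at most 96 school-by-grade cells, and 157/96 = 1.64 classes per cell as a minimum average.

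**3. One grade.** Let S schools contribute k = 26/S classes per year group (157/6 ≈ 26 classes per grade). Total variance is 1.
- From the plan: ICC 0.05 and 15 pupils per class, so pupil error of a class mean is 0.95/15 = 0.0633.
- Assumed: school variance 0.01, year-group variance v of 0.01–0.02, class variance 0.04 − v, and S.
- Write e = 0.04 − v + 0.0633.

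True variance of the contrast = (2/S)(v + e/k).

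The school-plus-class model pools two mean squares within schools: S − 1 degrees of freedom with expectation e + kv, and 2S(k−1) with expectation e. It therefore reports (2/26)(e + v·f), with f = k(S−1)/[S(2k−1) − 1]. With many schools the share of v that it picks up is f/k → 1/(2k−1), which is 1/3 at k = 2 and 1/9 at k = 5.

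False-positive rate = 2[1 − Φ(1.96/ratio)], where ratio = true SE / model SE.

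Example, S = 5 and v = 0.01: k = 5.2, e = 0.0933, f = 0.452.
- True variance = 0.4 × (0.01 + 0.0933/5.2) = 0.01118, SE 0.106.
- Model variance = (2/26)(0.0933 + 0.0045) = 0.00753, SE 0.087.
- Ratio 1.22, false-positive rate 10.8%.

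| Schools in the grade | v | True SE | Model SE | Ratio | False-positive rate |
|---|---|---|---|---|---|
| 12 | 0.01 | 0.094 | 0.087 | 1.08 | 6.8% |
| 12 | 0.02 | 0.099 | 0.086 | 1.15 | 8.9% |
| 5 | 0.01 | 0.106 | 0.087 | 1.22 | 10.8% |
| 5 | 0.02 | 0.120 | 0.084 | 1.42 | 16.9% |
| 3 | 0.01 | 0.118 | 0.086 | 1.36 | 15.0% |
| 3 | 0.02 | 0.141 | 0.083 | 1.68 | 24.4% |

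REML simulation (600 runs per setting, 3–5 schools) gave 12–26%. Analysis at year-group level gave 4–6%. At v = 0 or k = 1 the two formulas coincide and the ratio is 1.

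**4. Pooled over grades.** Cohorts B to E appear on both sides, so stable year-group differences largely cancel. The figures are large-sample, use the November 2023 and November 2024 waves, assume a within-pupil correlation of 0.6, and take v from 0.01 to 0.03. If every school holds all six cohorts and the model has grade terms, the SE ratio is:
- 1.02–1.06 at k = 2
- 1.04–1.12 at k = 3
- 1.08–1.22 at k = 5

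The false-positive rate is then 5.5–10.9%. Without grade terms the ratio is 1.00–1.04.

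**5. Further assumptions for the pooled estimate.** If schools hold only three cohorts each, the ratio with grade terms is 1.05–1.44 (6–17%). If year-group differences also shift between the two Novembers, with variance 0.005–0.01, the rate is about 12–21%. That last range is indicative only and is not rederived here.

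**The case against.** The best defence is that the size is assumed. The documents do not split the ICC, give a year-group variance, or state how many schools teach each grade. Section 2.3 argues that adjacent cohorts of a school come from much the same population. This stands as far as it goes: a reader might infer that the intervals are certainly too narrow, and the documents do not support that. They do not support zero year-group variance either, because similar socio-demographic make-up on average does not rule out chance differences between two particular year groups.

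A reader might also infer that year-group variance is simply averaged over the number of classes. It is not: the fitted class term takes up part of it, as step 3 shows. Nor does it follow that the overall 12-month answer is badly compromised. The pooled understatement is small to moderate and close to nil under one coding. The higher pooled figures need a school layout or a wave-to-wave shift that the documents do not state.

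Three narrower objections also have force.
- The 11–25% applies to grades taught in few schools. The plan's hypothesis concerns younger pupils, whose grades may be spread over more schools, where 7–9% is the relevant scenario.
- Grade subgroups could mean bands or an interaction, and could be applied to February 2024. That comparison is between schools and is not affected.
- The 12-school and 3–5-school scenarios are counts per grade. Five plus twelve exceeds the 16 schools unless some teach both stages.

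None of these supplies the missing level.

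**Conclusion.** The point holds as a conditional one. The model in 3.11 lacks the level at which exposure varies in the 12-month contrast, and parallel classes certainly exist. Whether intervals are materially too narrow depends on a year-group variance that only the data can show.

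With that variance at 0.01–0.02, single-grade tests run at about 7–9% with 12 schools and about 11–25% with 3–5, against a nominal 5%. With it at up to 0.03, the pooled estimate runs at about 5–11% when each school holds all six cohorts, depending on how the contrast is coded. The change should be made before analysis. The main reason is the grade-specific results.

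**What to change.** In 3.11:
- Write out the fixed part of the 12-month model, including whether it has grade terms.
- Add a random intercept for school-by-birth-cohort, between class and school. Add a year-group-by-wave term as a sensitivity analysis.
- For grade-specific contrasts, use small-sample degrees of freedom counted in school year groups. A paired comparison of school year-group means within grade is a simple check.
- If pupils change school between grades 7 and 8, define the unit for cohort C by the school attended at each wave, since those pupils are then not nested in one school-by-cohort unit.
- Keep coded (pseudonymous) school and class identifiers in the analysis dataset, and reconcile 4.5 with 3.11. Without those codes even the levels already listed cannot be fitted.

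No new data collection is needed. If the year-group variance is negligible, its estimate will be near zero and little is lost. Otherwise the intervals widen. The cost is clearest for single grades: a paired test on the true SEs in step 3, with S − 1 degrees of freedom and d = 0.16, has power of about 11–22% with 3–5 schools and 32–34% with 12. Single-grade contrasts that rest on few schools should be labelled exploratory.
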